 [REDACTED] FSH=follicle stimulating hormone; HBsAg=hepatitis B surface antigen; HBV=hepatitis B virus; HCV-Ab=hepatitis C virus antibody; HS=hidradenitis suppurativa clinical response; HIV=human immunodeficiency virus; HS=hidradenitis suppurativa; [REDACTED] hs-CRP=high-sensitivity C-reactive protein; IgG=immunoglobulin G; IgM anti-HBc=immunoglobulin M antibody to hepatitis B core antigen; IHS4=International Hidradenitis Suppurativa Severity Score System; IMP=Investigational Medicinal Product; IRT=interactive response technology; OX40L=OX40-Ligand; PD=pharmacodynamic(s); PK=pharmacokinetic(s); [REDACTED]; SAA=serum amyloid A; SAE=serious adverse event; SC=subcutaneous(ly); TB=tuberculosis; [REDACTED]  
 | V=visit; W=week; WOCBP=women of childbearing potential.

- a When several assessments take place at the same time, the following order should be respected: questionnaires, ECG, followed by vital signs, AE reporting, prior and concomitant medications, daily diary review, blood sampling, physical examination, lesion intervention if needed, HS clinical parameters, skin biopsy, and IMP administration.
- b A maximum of 28 days is required depending on participants' prior and concomitant medications. Randomization of the participant must take these constraints into consideration.
- c All visits are done on-site except if home nursing is arranged for visits at Week 18, 22, or 26. Participants in Denmark will not have home nursing, please refer to [Section 10.8.1.2](#).
- d Participants who discontinue IMP treatment prior to completing the 28-week treatment period and 8-week Follow-up Period will be evaluated as soon as possible at the individual participant's EOT Visit, using procedures as planned for the EOT Visit at Week 28 (Visit 16). At their EOT Visit, participants will resume their HS medications or other appropriate therapy as needed per Investigator discretion after the EOT study assessments have been performed and will enter the 8-week safety Follow-up Period, concluding with EOS Visit (Visit 17).
- e The study visits occur on the planned dates (relative to the first IMP), as scheduled.
- f Visits at Week 18, 22, and 26 may be performed with a home nursing service.
- g To qualify for randomization all inclusion criteria and none of the exclusion criteria are met by the participant.
- h Update inclusion/exclusion criteria, medical and surgical history, and prior and concomitant medications information to assure participant eligibility.

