- v* All eligible participants will be treated for 28 weeks, receiving a SC administration of IMP or placebo every 2 weeks for the first 14 weeks based on randomization, and then starting at Week 16 (Visit 10) all participants will receive IMP every 2 weeks until the last dose is administered at Week 26 (Visit 15).
- w* Per Investigator discretion, participants may resume treatment for HS as needed (including, but not limited to oral and topical antibiotics, corticosteroids, opioid and non-opioid analgesics, spironolactone, finasteride, or metformin). Participants may also receive unlimited lesion intervention as needed per Investigator discretion.
- x* Vital signs, including body temperature (°C), heart rate (beats per minute), respiratory rate (breaths per minute), and systolic and diastolic blood pressure (mm Hg), will be measured at all visits detailed in the flowchart.
- y* Physical examination will include examination of skin, nasal cavities, eyes, ears, cardiovascular, respiratory, gastrointestinal, neurological, lymphatic, and musculoskeletal systems. A brief symptom-directed physical examination should be performed at other visits if, in the opinion of the Investigator, it is warranted by the participant's AE status or on review of symptoms and will include, at a minimum, assessments of the skin, cardiovascular system, and abdomen (liver and spleen). Height will be measured and recorded at the Screening Visit. Weight will also be measured and recorded at the Screening, Baseline, Week 16, and EOS Visit.
- z* For fasting lipid panel, participant must be fasting for 8 hours prior to laboratory testing (may consume water). If unable to fast, participant may consume a light meal. Labs drawn during non-fasting laboratory testing will include hematology and clinical chemistry only. For laboratory testing please see [Table 12](#).
- aa* Only for WOCBP: serum pregnancy test at Screening (Visit 1) and urine pregnancy tests at every visit from Baseline (Visit 2) to EOS (Visit 17). A negative result must be obtained at Screening (Visit 1) and at Baseline (Visit 2) prior to randomization. In case of positive urine test, the study treatment will be withheld and a serum pregnancy test to confirm the pregnancy should be performed as soon as possible. Pregnancy will lead to definitive treatment discontinuation in all cases.

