Secondary endpoint- Skin pain	
Percentage of participants achieving at least 30% reduction and at least 1 unit reduction from Baseline in weekly average of daily HS Skin Pain NRS at Week 16 among participants with Baseline NRS = 3 (HS-Skin Pain NRS is based on worst skin pain in a 24-hour recall period [daily assessment is averaged over 7-day period])
	Biologic and small molecule immunosuppressive-naïve population of Period A	
The following IEs will be handled with the composite variable strategy; participants will be considered as non-responders after such IE.
 
 Using analgesic therapy within 5 days of Week 16 will be considered as non-responders Discontinuation of study intervention due to lack of efficacy. 
The following IE will be handled with the treatment policy strategy (without IEs that need to be handled with
	
CMH method including treatment group and stratified by baseline Hurley Stage.
 
The difference of the response rates between SAR442970 and placebo and the 80% and 90% confidence intervals will be derived.
 
Participants with missing data will be imputed as non-responder.

Endpoint Category	Estimands			
	Endpoint(s)	Population	Intercurrent event(s) handling strategy	Population-level summary and missing data handling
			
composite variable strategy). Data collected after starting such IE will be included.
 
• Discontinuation of study intervention due to reasons other than lack of efficacy.	

a The list of medications will be selected by blinded medical review prior to database lock. Participants that receive the selected treatment will also be reviewed in a blinded fashion to make sure the medication was used due for HS treatment failure and not an unrelated condition.

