Percentage of participants achieving HiSCR50 at Week 16 and other endpoints derived from HS clinical parameters (eg, HiSCR75, HiSCR90, IHS4, flares, DLQI, HiSQOL)	Immunosuppressive or immunomodulatory therapy Examples: natalizumab, rituximab, adalimumab, certolizumab pegol, etanercept, golimumab, infliximab, anakinra, canakinumab, bermekimab, ustekinumab, guselkumab, secukinumab, JAK inhibitors (e.g., abrocitinib, baricitinib, filgotinib, pacritinib, upadacitinib), or TYK inhibitors (e.g., brepocitinib deucravacitinib, ropsacitinib), or apremilast, corticosteroids, methotrexate, cyclosporine, retinoids, acitretin/etretinate, non-contraceptive hormonal therapy, zinc gluconate, intramuscular gamma globulin, colchicine, fumaric acid esters, or metformin (except for continuous treatment of pre-existing diabetes), or other systemic therapies that can also be used to treat HS.	No
	Antibiotic therapy Antibiotic therapy (topical and/or systemic [oral or IV]) for HS-related infection other than doxycycline or minocycline	Yes (CDGsn00892)
	Doxycycline or minocycline: Increase from stable dose established 28 days prior to baseline; or increase dose regimen greater than 100 mg PO BID for doxycycline or minocycline	Yes (CDGsn00892)
	Corticosteroid therapy Intralesional corticosteroids	No
	Corticosteroids for HS with systemic potential (e.g., injectable or high dose intralesional corticosteroids)	Yes (CDGsn00010)
Pain endpoints (HS skin pain NRS, PP NRS)	Analgesic therapy within 5 days preceding Week 16 visit Opioid analgesics and Non-opioid analgesics (e.g., antiepileptics (e.g., gabapentin), tricyclics (e.g., nortriptyline), or selective serotonin norepinephrine reuptake inhibitors (e.g., duloxetine, venlafaxine) other than ibuprofen or acetaminophen	Yes (CDGsn00195; CDGsn00229 ;CDGsn01761; CDGsn00009; CDGsn01793)
	Corticosteroid therapy Intralesional corticosteroids for HS	Yes (CDGsn00010)
	Incision and drainage procedure for HS	Yes (CMQ40194)

a When yes, if confirmed through blinded medical review the estimand for the intercurrent event handling strategy will be as follows: hypothetical for continuous endpoints, and composite for responder and time-to-event endpoints. When no, a treatment policy strategy will be applied.

Bayesian modeling

The following Bayesian logistic regression for the mean binary response will be used:

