The percentage of participants achieving at least 30% reduction and at least 1 unit reduction from Baseline in weekly average of daily HS Skin Pain NRS at Week 16 among participants with Baseline NRS ≥ 3 (HS-Skin Pain NRS is based on worst skin pain in a 24-hour recall period [daily assessment is averaged over 7-day period]) will be analyzed. Participants must have a minimum of 4 diary entries within the 7-day period prior to Week 16 to calculate the week's average. Those who don't meet this requirement will have missing data for that week.

The estimand for skin pain endpoint will be used and participants with missing data will be imputed as non-responders. The following IEs will be handled with the composite variable strategy; participants will be considered as non-responders after such IE.

- Using analgesic therapy within 5 days of Week 16 will be considered as non-responders.
- Starting selected prohibited medications. Participants that receive the selected treatment listed in Table 5 will be reviewed in a blinded fashion to make sure the medication was used due for HS treatment failure and not an unrelated condition.
- Discontinuation of study intervention due to lack of efficacy.

The following IE will be handled with the treatment policy strategy (without IEs that need to be handled with composite variable strategy). Data collected after starting such IE will be included.

- Discontinuation of study intervention due to reasons other than lack of efficacy.

Participants with missing data will be imputed as non-responders.

An estimate of the treatment difference (SAR442970 versus placebo) will be obtained using CMH method, stratified by baseline Hurley stage. The estimated treatment difference will be reported along with the 80% and 90% confidence intervals.

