Week 4	29	22 - 42	22 - 42		22 - 42
Week 6	43				
Week 8	57	43 - 70	43 - 70		43 - 70
Week 10	71				
Week 12	85	71 - 98	71 - 98		71 - 98
Week 14	99				
Week 16	113	99 - D ^b	99 - D ^b		99 - D ^b
Period B					
Week 18	15				
Week 20	29	2 - 42	2 - 42		2 - 42
Week 22	43				
Week 24	57	43 - 70	43 - 70		43 - 70
Week 26	71				
Week 28	85	>70	>70		>70

^a Day 1 in Period A is the day of the first blinded IMP administration (or the day of randomization for participant not exposed). Day 1 in Period B is the day of the first open-label IMP administration.

^b Last window in Period A is the 1st dose of open-label IMP administration.

Table 14 - Analysis window definition for daily questionnaires

Analysis visit	Targeted study day ^a	Time windows		
		Daily Diary HS-Skin Pain NRS	Daily Diary PP-NRS	Daily diary analgesic use
Period A				
Screening	-28 to -7	<-7	<-7	<-7
Baseline	1	-7 - <1	-7 - <1	-7 - <1
Week 2	15	8 - 14	8 - 14	8 - 14
Week 4	29	22 - 28	22 - 28	22 - 28
Week 6	43	36 - 42	36 - 42	36 - 42
Week 8	57	50 - 56	50 - 56	50 - 56
Week 10	71	64 - 70	64 - 70	64 - 70
Week 12	85	78 - 84	78 - 84	78 - 84
Week 14	99	92 - 98	92 - 98	92 - 98
Week 16	113	106 - D ^b	106 - D ^b	106 - D ^b
Period B				
Week 18	15	8 - 14	8 - 14	8 - 14
Week 20	29	22 - 28	22 - 28	22 - 28
Week 22	43	36 - 42	36 - 42	36 - 42
Week 24	57	50 - 56	50 - 56	50 - 56
Week 26	71	64 - 70	64 - 70	64 - 70
Week 28	85	78 - 84	78 - 84	78 - 84

a Day 1 in Period A is the day of the first blinded IMP administration (or the day of randomization for participant not exposed). Day 1 in Period B is the day of the first open-label IMP administration.

b D = minimum (Day 112, the day prior to the first open-label IMP)

Table 15 - Analysis windows for pharmacokinetics/pharmacodynamics variables

Analysis visit	Targeted study day ^a	Time windows				
		ADA	Blood biomarkers	PK	PD Biomarker	Skin Biopsy
Period A						
Screening	-28 to -14	<-14	<-14		<-14	
Baseline	1	-14 - 1	-14 - 1	≤1	-14 - 1	≤1
Week 2	15	2 - 21	2 - 21		2 - 21	
Week 4	29	22 - 42	22 - 42	2 - 49	22 - 42	
Week 6	43					
Week 8	57	43 - 70	43 - 70	50 - 63	43 - 70	
Week 10	71			64 - 77		
Week 12	85	71 - 98	71 - 98	78 - 98	71 - 98	
Week 14	99					
Week 16	113	99 - D ^b	> 1			
Period B						
Week 18	15			2 - 21		
Week 20	29	2 - 42	2 - 42	22 - 70	2 - 42	
Week 22	43					
Week 24	57	43 - 70	43 - 70		43 - 70	
Week 26	71					
Week 28	85	71 - 112	> 70	71 - 112	71 - 112	
Week 36	141	> 112		> 112	> 112	

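### Week 16 skin-pain response: early but permitted visits shorten the 7-day diary window to 4 to 6 days, and the SAP gives two conflicting analgesic rules

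*SAP*

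**What the plan says.** **Diary window.** SAP Section 2.3.3 defines response from the weekly average of the daily HS Skin Pain NRS. It states: "Participants must have a minimum of 4 diary entries within the 7-day period prior to Week 16". Anyone short of that has a missing score, and "participants with missing data will be imputed as non-responders". Table 14 in SAP Appendix 4 (Section 4.4) gives the Week 16 window for the pain, pruritus and analgesic diaries as Day 106 to D, where "D = minimum (Day 112, the day prior to the first open-label IMP" (footnote b). Day 1 is the first blinded dose.

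The protocol's Schedule of Activities puts the Week 16 visit at Day 113 with a tolerance of 3 days either way. Footnote v of Section 1.3.1 has dosing continue through the blinded period, "then starting at Week 16 (Visit 10) all participants will receive IMP every 2 weeks". Footnote e adds: "The study visits occur on the planned dates (relative to the first IMP), as scheduled".

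**Analgesic event.** The skin-pain row of SAP Table 3 lists, as a composite event, "Using analgesic therapy within 5 days of Week 16 will be considered as non-responders". Section 2.3.3 repeats this and then gives a separate bullet: "Starting selected prohibited medications. Participants that receive the selected treatment listed in Table 5 will be reviewed in a blinded fashion". Table 5, in its row for the pain endpoints, describes the event as "Analgesic therapy within 5 days preceding Week 16 visit Opioid analgesics and Non-opioid analgesics". It goes on to exclude ibuprofen and acetaminophen and makes the event subject to blinded medical review. Protocol Sections 6.9.1 and 6.9.2 allow ibuprofen and acetaminophen after Baseline, within dose limits.

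**The concern.** The start of the Week 16 diary window is fixed, but its end moves with the first open-label dose. A participant seen early, yet within the permitted tolerance, loses diary days while the 4-entry minimum stays the same. The number of missed entries that turns a participant into a non-responder then depends on the calendar day of the visit.

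On analgesics, the SAP states two rules for one event. Table 3 and the analgesic bullet in Section 2.3.3 name no drugs; Table 5 exempts two that the protocol permits. The anchor also differs: Week 16 in one place, the Week 16 visit in the other. Two programmers following different parts of the SAP could classify the same participant differently.

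Pain has its own secondary objective, so its responder rate should not turn on either ambiguity. The pruritus score (PP-NRS) shares the diary window and the 4-entry rule. The 5-day length of the look-back is a design choice and is not questioned.

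**Working it through.** **Step 1: diary days available.** Inputs: window start Day 106 and end D = min(112, v − 1) (SAP Table 14); permitted visit days 110 to 116 (protocol Schedule of Activities). I assume the first open-label dose, on Day v, is given on the Week 16 visit day. Days available = D − 106 + 1.

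| Dose day v | Window | Days | Missed entries tolerated |
|---|---|---|---|
| 110 | 106–109 | 4 | 0 |
| 111 | 106–110 | 5 | 1 |
| 112 | 106–111 | 6 | 2 |
| 113–116 | 106–112 | 7 | 3 |

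The plan's 7 days is reproduced for Days 113 to 116, not for Days 110 to 112.

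**Step 2: chance of a missing score.** The documents give no diary completion rate, so I take q per day as an assumption, independent between days. P(fewer than 4 entries) = Σ over k = 0 to 3 of C(n,k) qᵏ(1−q)ⁿ⁻ᵏ. For n = 4 this is 1 − q⁴; at q = 0.90, 1 − 0.6561 = 34.39%.

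| q | n = 4 | n = 5 | n = 6 | n = 7 | Summed excess over n = 7 |
|---|---|---|---|---|---|
| 0.95 | 18.55% | 2.26% | 0.22% | 0.02% | 20.97 points |
| 0.90 | 34.39% | 8.15% | 1.58% | 0.27% | 43.30 points |
| 0.80 | 59.04% | 26.27% | 9.89% | 3.33% | 85.20 points |

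**Step 3: extra imputed non-responders.** Let s be the share of visits on each of Days 110, 111 and 112 (assumed). Extra = 66 × s × summed excess. For s = 5% and q = 0.90: 66 × 0.05 × 0.4330 = 1.43.

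| q | s = 2% | s = 5% | s = 10% |
|---|---|---|---|
| 0.95 | 0.28 | 0.69 | 1.38 |
| 0.90 | 0.57 | 1.43 | 2.86 |
| 0.80 | 1.12 | 2.81 | 5.62 |

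These are upper limits. The endpoint is restricted to participants with Baseline NRS of at least 3, and status changes only for those who would otherwise respond. With 33 to 66 evaluable and 30% response (both assumed), the middle case becomes 1.43 × (33/66) × 0.30 = 0.2 to 1.43 × 0.30 = 0.4 participants reclassified.

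**Step 4: analgesic wording.** A participant who took only permitted ibuprofen or acetaminophen in the look-back and met the pain criterion is a non-responder under Table 3 and Section 2.3.3 read literally, but can be a responder under Table 5. Number reclassified = N × use × response, all assumed:

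- Central: 33 × 0.20 × 0.30 = 2.0; 66 × 0.20 × 0.30 = 4.0.
- Lowest: 33 × 0.10 × 0.20 = 0.7.
- Highest: 66 × 0.40 × 0.40 = 10.6.

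**Step 5: anchor day.** The Table 14 analgesic-diary window does not always contain the 5 days before the visit. It covers 4 of them for a visit on Day 110, all 5 for Days 111 to 113, and 4, 3 or 2 for Days 114, 115 or 116. The choice of anchor therefore matters whenever the visit is off Day 113.

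**The case against.** On the diary, Days 106 to 112 are the 7 days before the nominal Week 16 day, and footnote b only removes entries from the first open-label dose onward. That is sensible for a diary filled in each evening. Even the earliest permitted visit leaves 4 days, so the score is never missing by construction. Visits are expected on planned dates, and the number reclassified in the middle case is below one. The count of days and its effect on tolerated misses stand regardless; the objection limits the weight of this half, not its truth. The second term of footnote b matters only for doses on or before Day 112, so the SAP foresaw early dosing and shortened the window without moving its start.

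On analgesics, Table 5 is probably the intended definition. Its row is labelled for the pain endpoints, uses the same 5 days and carries drug-group codes, while Table 3 gives no list to program from. Reading the specific rule over the general one is natural. But the SAP does not say so: Table 3's pain row does not refer to Table 5, and Section 2.3.3 lists the Table 5 medications as a different event from analgesic use. The conflict remains on the page.

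The proposed window is also a hybrid. It follows the dose day for early visits and stays capped at Day 112 for late ones, where it covers 6, 5 or 4 of the 7 days before visits on Days 114 to 116. That is true and is accepted as the price of leaving late visits unchanged.

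**Conclusion.** Both points hold. The loss of diary days for open-label doses on Days 110 to 112 is exact, given dosing on the visit day. The disagreement between Table 3 and Section 2.3.3 on one side and Table 5 on the other is plain on reading.

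The size is uncertain and probably modest. The diary window is likely to affect few participants. The analgesic wording matters more, with 2 to 4 reclassified on central assumptions, but only if the literal reading is programmed. Visit shares, diary completion, independence between days, evaluable number, analgesic use and response rates are all assumptions.

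The scope is one secondary endpoint, plus PP-NRS for the diary window. No bias between arms is claimed and the primary endpoint is unaffected. With at most about 66 participants, a shift of a few can still visibly move a response rate, so both should be corrected before unblinding.

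**What to change.** (a) When the first open-label dose falls before Day 113, define the Week 16 diary window as the 7 days ending the day before that dose: Days 103–109, 104–110 or 105–111 for doses on Day 110, 111 or 112. Otherwise keep Days 106–112. Require at least 4 entries in either case, and use the same window for PP-NRS. The new windows do not overlap Week 14 (Days 92–98). At 90% completion, the chance of a missing score would be 0.3% for every permitted visit day.

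(b) Reconcile Table 3, Section 2.3.3 and Table 5 so that one analgesic event definition and one anchor day apply, for example by cross-reference to Table 5. Report the other definition as a supplementary analysis. This concerns only how the endpoint is derived, not what participants may take.

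The cost is SAP wording and derivation code; the diaries are already collected daily. For early visits the averaged days move back by up to 3 days, and there is one extra supplementary table.
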